#### **3.11.4 Procedures After Study Drug Treatment (Visit 16/Week 52)**

Patients who participate in the study in compliance with the protocol for at least 48 weeks of treatment will be considered to have completed the study. Patients who complete all study visits will be eligible for participation in a open-label study to assess the continued effectiveness and safety of IPP-201101 treatment.

If a patient is withdrawn from the study before completion of 48 weeks of study drug treatment, final evaluations will be performed at the last visit. To be evaluable for efficacy, a patient must be treated with at least 1 dose of study drug and must have all components of the SRI (baseline SLEDAI-2K total score, BILAG-2004 body system scores, and PhGA score) available. Patients with ongoing adverse events or clinically significant abnormal laboratory test results (as interpreted by the investigator) will be monitored as described in section 7.1.2 and section 7.2, respectively.

If a patient withdraws from the study during the treatment period, the reason must be determined and recorded on the patient's CRF (see section 4.3). For patients who withdraw consent, every attempt will be made to determine the reason. A blood sample for measurement of the concentration of IPP-201101 will be obtained from all patients who have an adverse event leading to withdrawal from the study and/or all patients who have a serious adverse event.

For patients who complete the study, final evaluations will be performed at visit 16 (week 52). For patients who withdraw prematurely from the study before completion of 48 weeks of study drug treatment, final evaluations will be performed at the last visit. The following procedures will be performed at visit 16 (week 52) or at early termination (before completion of the 48 weeks of study drug treatment), if applicable:

- physical examination
- clinical laboratory tests
- ANA
- anti-dsDNA Ab, C3, and C4
- anti-U1-70K snRNP Ab, anti-Sm Ab, CRP, IgG, IgM, IgE, IgA
- anti-IPP-201101 Ab (NOTE: Any patient with a positive test result for anti-IPP-201101 Ab at the final study visit will be followed with additional immunogenicity testing at 8-week intervals until the level returns to baseline value or the levels are judged by the investigator to be chronic, or the patient is lost to follow-up)
- vital signs measurements (includes systolic and diastolic blood pressures, pulse, and temperature)

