- an inability to reduce corticosteroid dose to the baseline dose or to withdraw therapy if the patient required a temporary increase in corticosteroid dose or a short course of corticosteroid treatment (ie, 2 weeks) and the medication is unable to be tapered to the baseline dose or be withdrawn, respectively
- therapy is initiated with pulse iv steroids
- an increase in the baseline dose of immunosuppressive agents (methotrexate, azathioprine, MMF)
- initiation of new immunosuppressive therapy (cyclophosphamide, methotrexate, azathioprine, cyclosporin, tacrolimus, leflunomide, MMF)
- initiation of therapy with biologics for the treatment of SLE
- any change in the doses of background therapies beginning with week 44 (visit 14) More information is provided in section 3.6 and Appendix B.

Patients will be excluded from participation in the study for any of the following reasons:

- they have been treated with iv pulse steroids within 4 weeks of the 1st dose of study drug
- they have received tacrolimus, cyclosporin A, or IVIG within 3 months of the 1st dose of study drug
- they have received cyclophosphamide or have been treated with biologic agents for SLE, such as fusion proteins, therapeutic proteins, or monoclonal antibodies or antibody fragments, within 6 months of the 1st dose of study drug
- they have received B-cell depleting agents such as rituximab or belimumab within one year of 1st dose of study drug and have not yet normalized the B-cell count
- they have a planned immunization with a live or live attenuated vaccine within 3 months prior to administration of the 1st dose of study drug and for 3 months after the last dose of study drug is administered

More information is provided in section 4.2 and Appendix B.

At each study center visit after the screening visit, the investigator will ask the patient whether any medications (other than study drug), including over-the-counter (OTC) medications, were taken since the previous visit (see Appendix B).

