## **6 ASSESSMENT OF EFFICACY**

## 6.1 Primary Efficacy Variable

The primary efficacy variable for this study is the proportion of patients achieving a combined clinical response using the SRI at week 52. An SRI response is defined as a reduction from baseline in the SLEDAI-2K score of at least 4 points, no worsening in PhGA (with worsening defined as an increase in PhGA of more than 0.30 point from baseline), no new BILAG A body system score, and no more than 1 new BILAG B body system score from baseline. The combined clinical response is intended to demonstrate an improvement in overall disease activity without worsening of disease in any organ system as determined by the investigator's quantitative and qualitative assessments.

The SLEDAI-2K is a validated objective measure that assesses disease activity within the last 28 days before completion of the index. It is a global index and includes 24 weighted clinical and laboratory variables. The total score (sum of all 24 scores) ranges from 0 to 105. A SLEDAI-2K score of 6 to 10 is indicative of moderate disease activity, and improvement is defined as a reduction of greater than 3 points ([Appendix C](#)). The SLEDAI-2K was chosen because it is an accepted scale for assessing disease activity, has been shown to be reliable and sensitive to change, and is easy for clinicians to use. The SLEDAI-2K should be administered at each visit throughout the study by the same physician assessor trained and qualified to use this scale.

The PhGA will be completed by the physician using a 3-inch visual analog scale (VAS) labeled from 0=none to 3=severe ([Appendix C](#)). This scale was chosen because it measures a domain of disease activity that may not be fully assessed in the other measures of disease activity. A change of greater than 0.3 point on the VAS indicates worsening. The PhGA should be administered at each visit throughout the study by the same physician assessor trained and qualified to use this scale.

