The BILAG-2004 is a validated objective and subjective global measure of the disease activity of SLE based upon the physician intention to treat and refers to disease activity within the last month prior to completion of the index. It includes 97 clinical and laboratory items to evaluate SLE disease activity in 9 organ systems; each organ system is assigned a score displayed as a grade from A to E, as follows: A=very active disease; B=patient needs increase in treatment for moderately active disease; C=stable or mild disease; D=previous organ involvement but no current disease activity; and E=no current disease activity and the organ system has never been involved ([Appendix D](#)). The BILAG-2004 was chosen because it is a reliable scale for evaluating SLE disease activity on the basis of the physician's intent to treat. The individual body system scores are evaluations of disease activity in individual organ systems that may be improving, worsening, or stable, and they provide information that is comparable and complementary to the SLEDAI-2K score. The BILAG-2004 should be administered at each visit throughout the study by the same physician assessor trained and qualified to use this scale.

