### **10.6.3 Planned Method of Analysis**

#### **10.6.3.1 Primary Efficacy Analysis**

The efficacy evaluation will be based on the full analysis set, which will include all patients who receive at least 1 dose of study drug. The statistical method to be used for the SRI is the logistic regression model with treatment and stratification factors as main factors. Patients who withdraw from the study are classified as nonresponders as measured by SRI at week 52 in the primary analysis. The SRI is linked to the model factors through the logit function. The

likelihood-ratio–based Chi-square statistics will be used for testing the treatment difference between IPP-201101 and placebo in SRI at week 52 at the significance level 0.05. The odds ratio (active/placebo) and associated 95% confidence interval will be determined from the logistic regression model.

As sensitivity analyses, the primary analysis will be repeated using another 3 imputation methods to estimate missing SRI at week 52 according to the reason for withdrawal. In the 1st method, patients who withdraw because of lack of efficacy will be classified as treatment failures assessed by SRI at week 52. For patients who withdraw because of other reasons, their missing SRI at week 52 will be estimated using the multiple imputation method (Little and Rubin, 2002). The imputation values will be drawn from the categories formed by treatment group and randomization stratum to which the patient belongs. In the 2nd method, the missing SRI at week 52 will be imputed using the last observation carried forward (LOCF) method. In the 3rd method, patients who withdraw and those completers who used prohibited medication within 8 weeks from week 52 will be classified as nonresponders.

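### The primary analysis overrides observed SRI only for withdrawal, so a completer with one of the protocol's own medication triggers can count as a responder

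*Protocol*

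**What the plan says.** **Primary rule.** Protocol section 10.6.3.1 states: "Patients who withdraw from the study are classified as nonresponders as measured by SRI at week 52 in the primary analysis". It names no other override. The SRI in section 10.6.1 is built from SLEDAI-2K, PhGA and BILAG, with no medication component. Secondary variables are only summarised descriptively (10.6.3.2), so week-52 SRI carries the only planned hypothesis test.

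**Third sensitivity method, same section.** "patients who withdraw and those completers who used prohibited medication within 8 weeks from week 52 will be classified as nonresponders". The synopsis repeats the three sensitivity methods but omits the primary rule for withdrawals.

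**Medication triggers.** Section 3.6 defines treatment failure largely by medication events and requires withdrawal. Section 5.2 has its own mandatory withdrawal list, which includes every alteration of a background dose from week 44 on. Both sections forbid steroids for flare or for non-SLE conditions from week 44 through week 52. Neither says how such a patient is scored in the analysis.

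**Timing.** Table 2 places visits 15 and 16 at weeks 48 and 52, with none between. At each visit, under section 5.2, "the investigator will ask the patient whether any medications (other than study drug), including over-the-counter (OTC) medications, were taken since the previous visit". Section 3.11.4 has the final procedures done at visit 16 "or at early termination (before completion of the 48 weeks of study drug treatment), if applicable". It also says that patients who take part "in compliance with the protocol for at least 48 weeks of treatment will be considered to have completed the study".

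**The concern.** The plan already uses a composite logic: a patient who leaves the study has failed, whatever the last score. It does not extend that logic to a patient who has the event that should have led to leaving but who reaches week 52. That patient is a responder if the observed SRI is met, and is reclassified only in a sensitivity analysis.

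The last four weeks matter most because they are also the window that the endpoint measures. SLEDAI-2K "assesses disease activity within the last 28 days before completion of the index", and BILAG-2004 "refers to disease activity within the last month prior to completion of the index". New treatment in that window may affect the score directly. At stake is whether responder status in the one confirmatory test follows from the recorded event or from the site's handling of it.

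**Working it through.** **1. Which analysis catches which patient**

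| Patient with a trigger under 3.6 or 5.2 | Primary analysis | Third method |
|---|---|---|
| Withdrawn by the site | Nonresponder | Nonresponder |
| Completer, use in weeks 44–52 | Observed SRI | Nonresponder |
| Kept in against 3.6/5.2, trigger before week 44 only | Observed SRI | Observed SRI |

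The third method's window starts at 52 − 8 = week 44. Use in weeks 44–48 can be learned at visit 15 (week 48), while withdrawal is still straightforward. Use after week 48 is normally learned at visit 16, the endpoint visit. The index look-back starts at week 52 minus 28 days, which is week 48, so the two windows coincide.

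The third row arises only if a site does not follow mandatory text. That is non-adherence, not a contradiction in the plan.

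**2. The plan's own power figures**

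Inputs (10.2): 100 evaluable patients per group, placebo 40% to 45%, differences of 25 and 20 points, Pearson chi-square, two-sided 0.05.

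Power = Φ[(d − 1.96·s0)/s1], with s0 = √(2·p̄(1−p̄)/n) and s1 = √([p1(1−p1) + p2(1−p2)]/n).

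- 40% vs 65%: s0 = 0.0706, s1 = 0.0684, (0.25 − 0.1384)/0.0684 = 1.63, power 94.9%.
- 40% vs 60%: s0 = 0.0707, s1 = 0.0693, (0.20 − 0.1386)/0.0693 = 0.89, power 81.2%.
- From a 45% placebo rate: 95.3% at 25 points and 81.6% at 20 points.

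These agree with the stated 90% or greater and 80%.

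**3. Illustration of size**

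The documents give no rate for such events. **Assumption:** 1 to 3 patients per 100 per arm. The planning rates are taken to count these patients as nonresponders, so the rule as written adds some of them back.

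- *Upper bound:* every such patient meets SRI.
- *Arm rate:* they meet SRI at their arm's rate. For example, at 3 on placebo and 1 on active, 40 + 3×0.40 = 41.2% and 65 + 1×0.65 = 65.65%.

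| Users per 100, placebo/active | Rates scored | Difference (points) | Power |
|---|---|---|---|
| None | 40 vs 65 | 25 | 94.9% |
| 3/1, upper bound | 43 vs 66 | 23 | 91.0% |
| 3/1, arm rate | 41.2 vs 65.65 | 24.45 | 94.0% |
| 3/3, upper bound | 43 vs 68 | 25 | 95.1% |
| 1/3, upper bound | 41 vs 68 | 27 | 97.4% |
| None | 40 vs 60 | 20 | 81.2% |
| 3/1, upper bound | 43 vs 61 | 18 | 72.5% |
| 3/1, arm rate | 41.2 vs 60.6 | 19.4 | 78.8% |

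The upper bound is generous. Section 6.1 defines a BILAG grade as "B=patient needs increase in treatment for moderately active disease", so many patients who needed added treatment would fail SRI anyway.

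If the planning rates instead describe observed SRI, the fix subtracts patients. An equal 2 per 100 gives 38% vs 63%, still 25 points, with power 94.8%.

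**The case against.** The strongest reply is that the protocol, read as a whole, already makes these patients nonresponders: 3.6, 5.2 and Appendix B require withdrawal, and 10.6.3.1 turns every withdrawal into nonresponse. Under full enforcement that is right. But the third method names completers with prohibited use, so the protocol itself does not expect enforcement to be complete.

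Four stronger readings are tempting, and the documents do not support them.

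- *That withdrawal cannot operate after week 48.* The late steroid ban runs through week 52, and final disposition is recorded at visit 16 (3.11.4 and Table 2), so a withdrawal could be entered there. What stands is that 3.11.4 describes early termination only before 48 weeks and treats 48 compliant weeks as completion. The result is therefore left to site action.
- *That the permissive verb in section 4.3 softens the withdrawal rules and opens a second gap before week 44.* That sentence is a pooled cross-reference, and some sections it lists (5.3, 7.1.6) are truly discretionary. Sections 3.6 and 5.2 remain mandatory, and 5.2 states the rule for failure to taper steroids twice.
- *That differences between the trigger lists create responders.* A leflunomide increase is in 3.6 and Appendix B but not in the 5.2 list. Failure to taper is in 5.2 but not in 3.6. A patient is withdrawn if either list is followed, so the differences are editorial.
- *That the rule inflates false positives.* With no drug effect in a blinded trial, expected use is equal in both arms.

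It is also fair to say that the main case is already reclassified in a prespecified sensitivity analysis, and that blinded review procedures usually sit in an SAP, which is not shown here. That limits severity. It does not remove the point, because the protocol itself fixes the primary rule and places the medication rule in sensitivity only.

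**Conclusion.** The point holds as a low-severity, cheap improvement. A completer with a medication trigger, most plausibly from use after week 48, can be a primary responder, and only a sensitivity analysis changes that. That weeks 48–52 are the main case is an inference from the visit schedule and the completer definition; the protocol's own window is weeks 44–52.

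All event rates are assumed. At the more realistic setting with a placebo excess, the loss is about 1 to 2 points of power. Only a 3-to-1 placebo excess in which every user meets SRI takes power to 91% (25 points) or 72.5% (20 points). Equal use leaves the difference essentially unchanged, and more use on active inflates it. The direction cannot be known from the document, and the test is not invalidated.

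**What to change.** In section 10.6.3.1, and in the synopsis, make the third-method rule the primary one. A full-analysis-set patient is a nonresponder if the patient withdraws, or has a recorded medication event through week 52 that is a withdrawal or treatment-failure trigger under 3.6 or 5.2, whether or not the site withdrew the patient. Determine this by blinded review of the concomitant-medication data before unblinding. Keep observed-SRI scoring of completers as the sensitivity analysis. Events before week 44 in patients kept in the study are then covered as a by-product.

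The sponsor must first reconcile the passages that define a trigger:

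- the 80 mg/week limit in 3.6 and 5.2 against the flare allowance in 5.2 of up to 30 mg/day for 2 weeks (30 × 7 = 210 mg/week);
- whether background dose reductions from week 44 count, since 5.2 covers changes of every kind;
- the leflunomide and taper differences between the lists;
- the completer definition in 3.11.4.

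No view is taken on which clinical rule is right.

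The cost is a sentence or two of analysis text, that reconciliation, and a blinded review of data already collected at every visit. Response rates would be slightly lower, by at most 1 to 3 points per arm under the assumed use.

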#### **10.6.3.2 Secondary Efficacy Analysis**

Secondary efficacy variables will be summarized using the descriptive statistics by treatment group and time point. Safety evaluations will include all patients who received at least 1 dose of study drug. Descriptive statistics will be used to summarize the safety variables.

### **10.7 Safety Variables and Analysis**

The safety analysis set (see section 9.3) will be used for all safety analyses.

#### **10.7.1 Study Drug Exposure**

Study drug exposure will be summarized by treatment group and stratification factors at baseline for all patients who received at least 1 dose of the study drug (safety analysis set) during the study. The exposure will be characterized by treatment duration and number of injections received. Treatment duration is the number of days from the 1st to the last dose.

#### **10.7.2 Safety Variables**

The overall safety and tolerability of IPP-201101 treatment will be assessed throughout the study by evaluating adverse events and the following additional safety variables:

- clinical laboratory (serum chemistry, hematology, and urinalysis) test results at each visit during the treatment period
- vital signs (systolic and diastolic blood pressures, pulse, temperature, and body weight) measurements at each visit during the treatment period
- 12-lead ECG findings at week 24 and the final assessment (or early termination) (week 52)
- suicidality using the C-SSRS at each visit during the treatment period
- adverse events that suggest an anaphylactic reaction to study drug during the treatment period

- physical examination findings, including physical examination symptom directed findings, at selected time points throughout the study
- concomitant medication usage throughout the study

### **10.7.3 Safety Analysis**

For continuous variables, descriptive statistics (n, mean, SD, median, minimum, and maximum) will be provided for actual values and changes from baseline to each time point, including endpoint. For categorical variables, patient counts and percentages will be provided. Descriptive summaries of serious adverse events, patient withdrawals because of adverse events, and clinically significant abnormal values (clinical laboratory or vital signs values) on the basis of predefined criteria will also be provided. Summaries will be presented by treatment group and for all patients.

All adverse events will be coded using the Medical Dictionary for Regulatory Activities (MedDRA). A patient will be counted only once in each preferred term or system organ class category for the analyses of safety. Summaries will be presented for all adverse events (overall and by severity), adverse events determined by the investigator to be treatment related (overall and by severity), serious adverse events, and adverse events causing withdrawal from the study. Summaries will be presented by treatment group and for all patients. Patient listings of deaths, other serious adverse events, and adverse events leading to withdrawal will be presented.

Changes in laboratory and vital signs measurement data will be summarized descriptively. All values will be compared to prespecified boundaries in order to identify clinically significant changes or values, and such values will be listed.

Newly occurring physical examination abnormalities will be identified and listed.

The use of concomitant medications will be summarized by therapeutic class using descriptive statistics. Concomitant medications will include all medications taken while the patient is treated with study drug. Concomitant medication usage will be summarized as present at screening, ongoing at baseline/start of study drug treatment (visit 2 [week 0]), and started any time after visit 2 (week 0) through visit 16 (week 52).

Cumulative positive C-SSRS outcomes during the study will be summarized by treatment group.

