In order to ensure patient safety, patients who are determined to be treatment failures will be withdrawn from the study. Patients may be treated for treatment failure at the discretion of the investigator. Treatment failure is defined as any of the following:

- occurrence of a severe flare according to the SFI (also results in withdrawal from the study)
- increase in use of background oral corticosteroids beyond 80 mg of prednisone equivalent/week. (NOTE: Treatment of mild/moderate flare is permitted as detailed in section 5.2. The use of steroids for the treatment of a mild or moderate flare or for the treatment of conditions other than SLE will not be permitted beginning at week 44 [visit 14] through week 52 [visit 16].)
- initiation of pulse iv steroid therapy (ie, 250 to 1000 mg iv total daily dose of methylprednisolone)
- increase in the dose of immunosuppressive agents (methotrexate, azathioprine, MMF, leflunomide) above the baseline level
- initiation of new immunosuppressive therapy (cyclophosphamide, methotrexate, azathioprine, cyclosporin, tacrolimus, leflunomide, MMF)

- initiation of therapy with biologics for the treatment of SLEte, azathioprine, cyclosporin, tacrolimus, leflunomide, MMF)

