### **7.1.2 Recording and Reporting Adverse Events**

For the purpose of adverse event recording, the study period is defined as that time period from signature of the informed consent form through the end of the final assessment. All adverse events that occur during the study period must be recorded on the CRF, regardless of the severity of the event or judged relationship to the study drug. For serious adverse events, the Serious Adverse Event Transmittal Form must also be completed and the serious adverse event reported immediately (see section 7.1.5). Any reported serious adverse event that occurs after the study follow-up period (regardless of time after study participation) will be assessed for its relationship to the study drug or to the patient’s participation in the study. If a serious adverse event occurs after the study follow-up period and is considered related to the study drug or a study procedure by the investigator, it must be recorded on the Serious Adverse Event Transmittal Form and reported immediately.

At each contact with the patient, the investigator must query the patient for adverse events by asking an open-ended question such as, “Have you had any unusual symptoms or medical problems since the last visit? If yes, please describe.” All reported or observed signs and symptoms will be recorded individually, except when considered manifestations of a medical condition or disease state. A precise diagnosis will be recorded whenever possible. When such a diagnosis is made, all related signs, symptoms, and any test findings will be recorded collectively as a single diagnosis on the Serious Adverse Event Transmittal Form and on the CRF.

The clinical course of each adverse event will be monitored at suitable intervals until resolved or stabilized, until the patient is referred to the care of a local health care professional, or until a determination of a cause unrelated to the study drug or study procedure is made.

The onset and end dates, duration, action taken regarding study drug, treatment administered, and outcome for each adverse event must be recorded on the CRF. The relationship of each adverse event to study drug treatment and study procedures, and the severity and seriousness of each adverse event, as judged by the investigator, must be recorded as described below.

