#### **7.1.7 Withdrawal From the Study Due to Severe Flares**

A patient will be withdrawn from the study for a severe lupus flare as per the SFI as described in section 3.6.

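### Adverse events are tabulated as crude patient percentages although withdrawal for flare or treatment failure ends recording early; add exposure-adjusted rates beside them

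*Protocol*

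**What the plan says.** **The measure.** Section 10.7.3 summarises safety by treatment group: "For categorical variables, patient counts and percentages will be provided". For coded events, "A patient will be counted only once in each preferred term or system organ class category for the analyses of safety". The safety set in section 10.3 is everyone who took at least one dose. Section 10.6.3.2 confirms that the intent is descriptive: "Descriptive statistics will be used to summarize the safety variables".

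**Withdrawal.** Section 3.6 says that "patients who are determined to be treatment failures will be withdrawn from the study", and section 7.1.7 that "A patient will be withdrawn from the study for a severe lupus flare as per the SFI". Section 5.2 repeats most of these triggers. In each case the patient leaves the study, not only the study drug.

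**The recording window.** Section 7.1.2 sets it for adverse events: "the study period is defined as that time period from signature of the informed consent form through the end of the final assessment". Section 3.11.4 says that for patients who leave before completing 48 weeks of treatment, "final evaluations will be performed at the last visit".

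**What is still captured later.** Section 7.1.2 keeps one route open: "If a serious adverse event occurs after the study follow-up period and is considered related to the study drug" or a study procedure, it must still be reported. Sections 4.3 and 7.1.6 continue the follow-up of events that caused withdrawal.

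**What else is shown by arm.** Section 10.7.1 summarises exposure as days from first to last dose and number of injections. Section 10.5 and its subsection 10.5.1 summarise withdrawals by reason and treatment group.

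**The concern.** Taken together, these sections make the length of adverse-event observation depend on efficacy, while the stated measure takes no account of it. A patient withdrawn for treatment failure at week 8 counts in the denominator exactly like one observed to week 52. New non-serious events and new unrelated serious events after withdrawal are not collected.

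With equal true event rates, the arm that loses more patients to failure would show lower percentages for events other than lupus worsening. On the sizing hypothesis in section 10.2 that arm is placebo, so IPP-201101 would appear to carry a small excess that is only longer observation. If failures ran the other way, a real excess on IPP-201101 would be partly hidden. Sections 1.3.2 and 1.4 say that data on long-term immune effects are insufficient, so the 52-week harm comparison matters here.

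**Working it through.** **The plan's own figures.** The protocol gives no adverse-event risk, withdrawal rate or follow-up time for this trial. Its only design figure is efficacy power, which reproduces. With 100 per group, two-sided alpha 0.05 and the pooled normal approximation, power is 94.9% for 40% vs 65% and 81.2% for 40% vs 60%. This confirms the response rates used below; the point itself does not depend on it.

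**Illustration 1: an event with a true 52-week risk of 20% in both arms.** Response is 40% on placebo and 65% on active (40% plus the 25-point difference in section 10.2). The remaining inputs are assumptions: a share w of nonresponders withdraws, evenly over 52 weeks; the event hazard is constant and equal in both arms; recording stops at withdrawal.

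- Withdrawn proportion: q = w × (1 − response).
- Share of the 52-week window lost: q/2.
- Cumulative hazard: l = −ln(1 − 0.20) = 0.2231.
- Observed risk in a withdrawn patient: 1 − (1 − e^(−l))/l = 1 − 0.20/0.2231 = 0.1037.
- Percentage shown: (1 − q) × 0.20 + q × 0.1037.

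At w = 1/3 on placebo, q = 0.20, giving 0.80 × 0.20 + 0.20 × 0.1037 = 18.1%. On active, q = 0.1167, giving 18.9%.

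| w | q, placebo / active | window lost | shown, placebo / active | spurious difference |
|---|---|---|---|---|
| 1/3 | 20.0% / 11.7% | 10.0% / 5.8% | 18.1% / 18.9% | 0.8 points |
| 1/2 | 30.0% / 17.5% | 15.0% / 8.8% | 17.1% / 18.3% | 1.2 points |
| 3/4 | 45.0% / 26.3% | 22.5% / 13.1% | 15.7% / 17.5% | 1.8 points |

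**Illustration 2: a common event.** Section 1.3.2.3 reports adverse events in 65 of 150 patients (43.3%) in study IP-004. Reading this as a 24-week risk is an assumption. The hazard is then h = −ln(1 − 0.433)/24 per week, about 123 first events per 100 patient-years. Withdrawal is taken as exponential with λ = −ln(1 − W)/52, where W is the assumed proportion withdrawn by week 52. The percentage shown is h/(h + λ) × (1 − e^(−52(h + λ))).

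| W, fewer / more withdrawals | any adverse event shown | spurious difference |
|---|---|---|
| 10% / 10% | 67.9% / 67.9% | 0 |
| 10% / 20% | 67.9% / 64.8% | 3.0 points |
| 15% / 30% | 66.4% / 61.6% | 4.7 points |
| 20% / 40% | 64.8% / 58.2% | 6.6 points |
| 10% / 40% | 67.9% / 58.2% | 9.6 points |

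Differences are taken before rounding. For an event with 10% risk under full follow-up, the four unequal rows give 0.5 to 1.6 points. Under this model a rate per unit of person-time equals h in both arms in every row.

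**Masking.** With 40% vs 20% withdrawn and a 10% event, a true hazard ratio of about 1.15 against the arm with more withdrawals would show as equal percentages, 9.0% in each arm.

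**Do the other tables repair this?** The exposure summary stops at last dose, whereas a completer's event window runs about four weeks longer, to week 52. Neither that summary nor withdrawals by reason enters the event figures. They would reveal an imbalance but not correct for it.

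**The case against.** The strongest reply is that exposure-adjusted rates are ordinary SAP content, that section 10.11 refers to a complete statistical plan, and that 10.7.3 nowhere rules rates out. This stands against saying that percentages are the only measure that will ever be produced, which a reader might infer: the protocol names no other for adverse events, but it does not exclude one. It does not dispose of the point, because the protocol itself states a measure suited to equal follow-up alongside rules that make follow-up unequal.

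A reader might also infer that the failing arm will simply look safer. The documents do not support that. Section 7.1.1 counts significant worsening of the disease under study as an adverse event, and hospitalisation makes an event serious under 7.1.5.1. The flares that force withdrawal can therefore add events to the failing arm. Nor is it known which arm will fail more: section 1.3.2.4 reports a trend against active in an earlier study, though with another formulation.

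Late serious events judged related must still be reported, so the loss concerns new non-serious events and new unrelated serious events.

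The size is modest. With 100 per arm and a risk near 18%, the 95% half-width for a difference is 1.96 × √(2 × 0.18 × 0.82/100) = 10.6 points, so 1.8 points is under one fifth of it. The display is descriptive, with no test attached.

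Finally, rates have their own weakness. For events clustered at the first doses, longer person-time dilutes the rate in the better-retained arm, and withdrawal for flare may be related to event risk. This rules out reading harm from the rates alone.

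**Conclusion.** The point holds as a conditional one. If severe flare or treatment failure is more frequent in one arm, that arm is observed for less time, and its crude percentages for events other than lupus worsening are too low relative to the other arm. For a 20% event the artefact is 0.8 to 1.8 percentage points under the stated assumptions. For any adverse event it is about 3 to 10 points if withdrawal differs by 10 to 30 points. All these sizes rest on assumed withdrawal rates, a constant hazard equal in both arms, and withdrawal independent of event risk. The distortion is not large enough to undermine the safety evaluation, but it can be avoided with dates that the trial already collects, and a supplementary analysis is best fixed before unblinding.

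**What to change.** In section 10.7.3, or in the SAP with a reference from there:

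- Keep the counts and percentages.
- Add, for all, related and serious adverse events, incidence rates by arm: patients with a first event per 100 patient-years. Person-time runs from first dose to first event or final assessment, not to last dose.
- Give the between-arm rate difference with a 95% confidence interval for any adverse event and any serious adverse event.
- Present events that are lupus worsening separately from the rest.
- State that the rates are read beside the percentages, not in place of them.

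The cost is a few sentences and a few tables. Onset dates (7.1.2) and withdrawal dates (4.3) already go on the CRF, and dosing dates are needed for the exposure summary in 10.7.1. The downside is that the rates assume a roughly constant hazard and withdrawal unrelated to event risk, which should be stated with the tables. No withdrawal or clinical rule needs to change.
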